4.2.3.2 Second Supplementary Analysis

The MMRM model assumes that the errors are normally distributed. When the assumption of normal error distribution is violated, the model standard errors may be over-estimated.

The assumption of normality in the main analysis will be assessed visually by residual plots (Q-Q plot and plot of residuals against predicted values). If the plots indicate lack of normality, the main analysis will be repeated but WASO will be log-transformed and the variable change from baseline in log WASO at week 4 and week 12 will be analyzed.

The WASO value at each night will be log-transformed before calculating the mean value at each visit (see Section 4.2.1). The change from baseline in log WASO at week 4 and week 12 will be calculated as follows:

log WASO mean value at week 4/12 – log WASO mean value at baseline

The same analysis steps in alignment with the primary estimand strategy for ICEs (Section 4.2.2) will be implemented. In the MMRM model, baseline WASO value will be the baseline log WASO value instead.

The overall treatment effects will be back transformed into the original scale to report the geometric mean ratio to baseline for each study treatment and the geometric mean ratio for elinzanetant / placebo and corresponding 90% CIs. Q-Q plot and plot of residuals against predicted values will be produced to check the assumption of normality on the analysis of log-transformed data.

4.3 Secondary Endpoints Analysis

4.3.1 Secondary PSG Endpoints

- Change from baseline in WASO at week 12 as measured by PSG
- Change from baseline in sleep efficiency (SE) at week 4 as measured by PSG
- Change from baseline in SE at week 12 as measured by PSG

Version 2.0 Page: 25 of 57

The secondary PSG endpoints will be calculated analogous to the primary endpoint (Section 4.2.1). See Section 6.2.1 for more details on the definition for each parameter as measured by PSG.

4.3.1.1 Change from Baseline in WASO at Week 12

Change from baseline in WASO at week 12 will be analyzed in the same MMRM model as the primary endpoint for the main analysis and for the supplementary analyses (Section 4.2.2. and 4.2.3).

4.3.1.2 Change from Baseline in Sleep Efficiency (SE) at Week 4 and 12

For the analysis of change from baseline in SE at week 4 and week 12, the ICEs will be handled according to the treatment policy and no missing data imputation is planned. The actual values and change from baseline in SE will be summarized using descriptive statistics by study treatment and week using the FAS.

The change from baseline over time by study treatment will be shown using line plots for means and 95% CI. In addition, descriptive statistics for actual values and change from baseline in SE will be summarized by study treatment and individual nights (i.e., baseline night 1, baseline night 2, week 4 night 1, week 4 night 2, week 12 night 1, week 12 night 2).

The descriptive statistics for the actual and change from baseline in WASO by study treatment and week will also be summarized using the SLAS.

4.3.2 Secondary PRO Endpoints

- Change from baseline in PROMIS SD SF 8b total score at week 4
- Change from baseline in PROMIS SD SF 8b total score at week 12
- Change from baseline in ISI total score at week 4
- Change from baseline in ISI total score at week 12

For all secondary PRO endpoints, the ICEs will be handled according to the treatment policy. No missing data imputation is planned for these endpoints. Analyses will be performed using the FAS.

4.3.2.1 Patient-reported Outcomes Measurement Information System Sleep Disturbance Short Form 8b (PROMIS SD SF 8b)

The PROMIS SD SF 8b includes 8 items assessing sleep disturbance over the past 7 days (Yu et al, 2011). Items assess sleep quality, sleep depth and restoration associated with sleep, perceived difficulties with getting to sleep or staying asleep and perceptions of the adequacy of and satisfaction with sleep. Participants respond to the items on a 5-point scale (scored from 1 to 5) from "not at all", "never", "very poor" to "very much", "always" or "very good". Four of the items are scored reversely.

Participants' responses to the 8 items of the instrument are scored on a 1-5 numeric rating scale and will be aggregated to derive total raw scores ranging from 8-40 with higher scores indicating greater severity of sleep disturbance. All PROMIS SD SF 8b items must be answered to produce a valid total score.

Version 2.0 Page: 26 of 57

These total raw scores will be converted into T-scores for comparison with population norms (United States general population). The conversion table is provided in Table 4-4. (PROMISSleep Disturbance – Scoring Manual).

Table 4-4: PROMIS Sleep Disturbance 8b - Conversion Table

Short Form Conversion Table Raw Score T-score SE* 8 28.9 4.8 9 33.1 3.7 10 35.9 3.3 11 38.0 3.0 12 39.8 2.9 13 41.4 2.8 14 42.9 2.7 15 44.2 2.7 16 45.5 2.6 17 46.7 2.6 19 49.0 2.6 20 50.1 2.5 21 51.2 2.5 22 52.2 2.5 23 53.3 2.5 24 54.3 2.5 25 55.3 2.5 26 56.3 2.5 27 57.3 2.5 28 58.3 2.5 29 59.4 2.5 30 60.4 2.5 31 61.5 2.5	Sleep Disturbance 8b				
8 28.9 4.8 9 33.1 3.7 10 35.9 3.3 11 38.0 3.0 12 39.8 2.9 13 41.4 2.8 14 42.9 2.7 15 44.2 2.7 16 45.5 2.6 17 46.7 2.6 19 49.0 2.6 20 50.1 2.5 21 51.2 2.5 22 52.2 2.5 23 53.3 2.5 24 54.3 2.5 25 55.3 2.5 26 56.3 2.5 27 57.3 2.5 28 58.3 2.5 29 59.4 2.5 30 60.4 2.5 31 61.5 2.5 32 62.6 2.5 33 63.7 2.6 34 64.9 2.6 35 66.1 2.7 36 67.5 2.8 37 69.0 3.0	Short Form Conversion Table				
9 33.1 3.7 10 35.9 3.3 11 38.0 3.0 12 39.8 2.9 13 41.4 2.8 14 42.9 2.7 15 44.2 2.7 16 45.5 2.6 17 46.7 2.6 18 47.9 2.6 19 49.0 2.6 20 50.1 2.5 21 51.2 2.5 22 52.2 2.5 23 53.3 2.5 24 54.3 2.5 25 55.3 2.5 26 56.3 2.5 27 57.3 2.5 28 58.3 2.5 29 59.4 2.5 30 60.4 2.5 31 61.5 2.5 32 62.6 2.5 33 63.7 2.6 34 64.9 2.6 35 66.1 2.7 36 67.5 2.8 37 69.0 3.0	Raw Score	T-score	SE*		
10 35.9 3.3 11 38.0 3.0 12 39.8 2.9 13 41.4 2.8 14 42.9 2.7 15 44.2 2.7 16 45.5 2.6 17 46.7 2.6 18 47.9 2.6 19 49.0 2.6 20 50.1 2.5 21 51.2 2.5 22 52.2 2.5 23 53.3 2.5 24 54.3 2.5 25 55.3 2.5 24 54.3 2.5 25 55.3 2.5 26 56.3 2.5 27 57.3 2.5 28 58.3 2.5 29 59.4 2.5 30 60.4 2.5 31 61.5 2.5 32 62.6 2.5	8	28.9			
11 38.0 3.0 12 39.8 2.9 13 41.4 2.8 14 42.9 2.7 15 44.2 2.7 16 45.5 2.6 17 46.7 2.6 18 47.9 2.6 19 49.0 2.6 20 50.1 2.5 21 51.2 2.5 22 52.2 2.5 23 53.3 2.5 24 54.3 2.5 25 55.3 2.5 26 56.3 2.5 27 57.3 2.5 28 58.3 2.5 29 59.4 2.5 30 60.4 2.5 31 61.5 2.5 32 62.6 2.5 33 63.7 2.6 34 64.9 2.6 35 66.1 2.7	9	33.1	3.7		
12 39.8 2.9 13 41.4 2.8 14 42.9 2.7 15 44.2 2.7 16 45.5 2.6 17 46.7 2.6 18 47.9 2.6 19 49.0 2.6 20 50.1 2.5 21 51.2 2.5 22 52.2 2.5 23 53.3 2.5 24 54.3 2.5 25 55.3 2.5 26 56.3 2.5 27 57.3 2.5 28 58.3 2.5 29 59.4 2.5 30 60.4 2.5 31 61.5 2.5 32 62.6 2.5 33 63.7 2.6 34 64.9 2.6 35 66.1 2.7 36 67.5 2.8	10	35.9	3.3		
13 41.4 2.8 14 42.9 2.7 15 44.2 2.7 16 45.5 2.6 17 46.7 2.6 18 47.9 2.6 19 49.0 2.6 20 50.1 2.5 21 51.2 2.5 22 52.2 2.5 23 53.3 2.5 24 54.3 2.5 25 55.3 2.5 26 56.3 2.5 27 57.3 2.5 28 58.3 2.5 29 59.4 2.5 30 60.4 2.5 31 61.5 2.5 32 62.6 2.5 33 63.7 2.6 34 64.9 2.6 35 66.1 2.7 36 67.5 2.8 37 69.0 3.0	11	38.0	3.0		
14 42.9 2.7 15 44.2 2.7 16 45.5 2.6 17 46.7 2.6 18 47.9 2.6 19 49.0 2.6 20 50.1 2.5 21 51.2 2.5 22 52.2 2.5 23 53.3 2.5 24 54.3 2.5 25 55.3 2.5 26 56.3 2.5 27 57.3 2.5 28 58.3 2.5 29 59.4 2.5 30 60.4 2.5 31 61.5 2.5 32 62.6 2.5 33 63.7 2.6 34 64.9 2.6 35 66.1 2.7 36 67.5 2.8 37 69.0 3.0	12	39.8	2.9		
15 44.2 2.7 16 45.5 2.6 17 46.7 2.6 18 47.9 2.6 19 49.0 2.6 20 50.1 2.5 21 51.2 2.5 22 52.2 2.5 23 53.3 2.5 24 54.3 2.5 25 55.3 2.5 26 56.3 2.5 27 57.3 2.5 28 58.3 2.5 29 59.4 2.5 30 60.4 2.5 31 61.5 2.5 32 62.6 2.5 33 63.7 2.6 34 64.9 2.6 35 66.1 2.7 36 67.5 2.8 37 69.0 3.0	13	41.4	2.8		
16 45.5 2.6 17 46.7 2.6 18 47.9 2.6 19 49.0 2.6 20 50.1 2.5 21 51.2 2.5 22 52.2 2.5 23 53.3 2.5 24 54.3 2.5 25 55.3 2.5 26 56.3 2.5 27 57.3 2.5 28 58.3 2.5 29 59.4 2.5 30 60.4 2.5 31 61.5 2.5 32 62.6 2.5 33 63.7 2.6 34 64.9 2.6 35 66.1 2.7 36 67.5 2.8 37 69.0 3.0	14	42.9	2.7		
16 45.5 2.6 17 46.7 2.6 18 47.9 2.6 19 49.0 2.6 20 50.1 2.5 21 51.2 2.5 22 52.2 2.5 23 53.3 2.5 24 54.3 2.5 25 55.3 2.5 26 56.3 2.5 27 57.3 2.5 28 58.3 2.5 29 59.4 2.5 30 60.4 2.5 31 61.5 2.5 32 62.6 2.5 33 63.7 2.6 34 64.9 2.6 35 66.1 2.7 36 67.5 2.8 37 69.0 3.0	15	44.2	2.7		
18 47.9 2.6 19 49.0 2.6 20 50.1 2.5 21 51.2 2.5 22 52.2 2.5 23 53.3 2.5 24 54.3 2.5 25 55.3 2.5 26 56.3 2.5 27 57.3 2.5 28 58.3 2.5 29 59.4 2.5 30 60.4 2.5 31 61.5 2.5 32 62.6 2.5 33 63.7 2.6 34 64.9 2.6 35 66.1 2.7 36 67.5 2.8 37 69.0 3.0	16	45.5			
19 49.0 2.6 20 50.1 2.5 21 51.2 2.5 22 52.2 2.5 23 53.3 2.5 24 54.3 2.5 25 55.3 2.5 26 56.3 2.5 27 57.3 2.5 28 58.3 2.5 29 59.4 2.5 30 60.4 2.5 31 61.5 2.5 32 62.6 2.5 33 63.7 2.6 34 64.9 2.6 35 66.1 2.7 36 67.5 2.8 37 69.0 3.0	17	46.7	2.6		
20 50.1 2.5 21 51.2 2.5 22 52.2 2.5 23 53.3 2.5 24 54.3 2.5 25 55.3 2.5 26 56.3 2.5 27 57.3 2.5 28 58.3 2.5 29 59.4 2.5 30 60.4 2.5 31 61.5 2.5 32 62.6 2.5 33 63.7 2.6 34 64.9 2.6 35 66.1 2.7 36 67.5 2.8 37 69.0 3.0	18	47.9	2.6		
21 51.2 2.5 22 52.2 2.5 23 53.3 2.5 24 54.3 2.5 25 55.3 2.5 26 56.3 2.5 27 57.3 2.5 28 58.3 2.5 29 59.4 2.5 30 60.4 2.5 31 61.5 2.5 32 62.6 2.5 33 63.7 2.6 34 64.9 2.6 35 66.1 2.7 36 67.5 2.8 37 69.0 3.0	19	49.0	2.6		
22 52.2 2.5 23 53.3 2.5 24 54.3 2.5 25 55.3 2.5 26 56.3 2.5 27 57.3 2.5 28 58.3 2.5 29 59.4 2.5 30 60.4 2.5 31 61.5 2.5 32 62.6 2.5 33 63.7 2.6 34 64.9 2.6 35 66.1 2.7 36 67.5 2.8 37 69.0 3.0	20		2.5		
23 53.3 2.5 24 54.3 2.5 25 55.3 2.5 26 56.3 2.5 27 57.3 2.5 28 58.3 2.5 29 59.4 2.5 30 60.4 2.5 31 61.5 2.5 32 62.6 2.5 33 63.7 2.6 34 64.9 2.6 35 66.1 2.7 36 67.5 2.8 37 69.0 3.0	21	51.2	2.5		
24 54.3 2.5 25 55.3 2.5 26 56.3 2.5 27 57.3 2.5 28 58.3 2.5 29 59.4 2.5 30 60.4 2.5 31 61.5 2.5 32 62.6 2.5 33 63.7 2.6 34 64.9 2.6 35 66.1 2.7 36 67.5 2.8 37 69.0 3.0	22	52.2	2.5		
25 55.3 2.5 26 56.3 2.5 27 57.3 2.5 28 58.3 2.5 29 59.4 2.5 30 60.4 2.5 31 61.5 2.5 32 62.6 2.5 33 63.7 2.6 34 64.9 2.6 35 66.1 2.7 36 67.5 2.8 37 69.0 3.0	23	53.3	2.5		
26 56.3 2.5 27 57.3 2.5 28 58.3 2.5 29 59.4 2.5 30 60.4 2.5 31 61.5 2.5 32 62.6 2.5 33 63.7 2.6 34 64.9 2.6 35 66.1 2.7 36 67.5 2.8 37 69.0 3.0	24	54.3	2.5		
27 57.3 2.5 28 58.3 2.5 29 59.4 2.5 30 60.4 2.5 31 61.5 2.5 32 62.6 2.5 33 63.7 2.6 34 64.9 2.6 35 66.1 2.7 36 67.5 2.8 37 69.0 3.0	25	55.3	2.5		
28 58.3 2.5 29 59.4 2.5 30 60.4 2.5 31 61.5 2.5 32 62.6 2.5 33 63.7 2.6 34 64.9 2.6 35 66.1 2.7 36 67.5 2.8 37 69.0 3.0	26	56.3	2.5		
29 59.4 2.5 30 60.4 2.5 31 61.5 2.5 32 62.6 2.5 33 63.7 2.6 34 64.9 2.6 35 66.1 2.7 36 67.5 2.8 37 69.0 3.0	27	57.3	2.5		
30 60.4 2.5 31 61.5 2.5 32 62.6 2.5 33 63.7 2.6 34 64.9 2.6 35 66.1 2.7 36 67.5 2.8 37 69.0 3.0	28	58.3	2.5		
31 61.5 2.5 32 62.6 2.5 33 63.7 2.6 34 64.9 2.6 35 66.1 2.7 36 67.5 2.8 37 69.0 3.0	29	59.4	2.5		
32 62.6 2.5 33 63.7 2.6 34 64.9 2.6 35 66.1 2.7 36 67.5 2.8 37 69.0 3.0	30	60.4	2.5		
33 63.7 2.6 34 64.9 2.6 35 66.1 2.7 36 67.5 2.8 37 69.0 3.0	31	61.5	2.5		
34 64.9 2.6 35 66.1 2.7 36 67.5 2.8 37 69.0 3.0	32	62.6	2.5		
35 66.1 2.7 36 67.5 2.8 37 69.0 3.0	33	63.7	2.6		
36 67.5 2.8 37 69.0 3.0	34	64.9	2.6		
36 67.5 2.8 37 69.0 3.0	35	66.1	2.7		
	36	67.5			
38 70.8 3.2	37	69.0	3.0		
	38	70.8	3.2		
39 73.0 3.5	39	73.0	3.5		
40 76.5 4.4	40	76.5	4.4		

*SE = Standard Error on T-score metric

PROMIS SD SF 8b is collected weekly per the SOA in the protocol (Section 1.3 of protocol). Weekly and EoT assessments will be assigned to study week taking the recall period of 7 days into account, i.e., an assessment will be assigned to that study week that covers the majority of the recall period (see Table 4-5). For example, an assessment performed on day 8 will be assigned to week 0, as the recall period covers days 1 to 7, which matches week 0. An assessment performed on day 12 will be assigned to week 1, as the recall period covers days 5 to 11, of which 3 days belong to week 0 and 4 days belong to week 1. If more than one assessment is assigned to a week, e.g., participant completes a weekly assessment and very shortly has a protocol scheduled visit (including EoT), the latest available assessment will be used in the analysis.

The baseline value will be the earliest assessment on day 1 or day 2. If both day 1 and day 2 assessment is not available, the baseline value will be the latest available assessment on or

Version 2.0 Page: 27 of 57

before day 4. Only assessments where \geq 4 days of the 7-day recall period are outside of the impact duration of prohibited hormonal therapies and medication potentially confounding efficacy will be included. Details regarding the prohibited medications together with the impact duration are described in Section 6.3.

Table 4-5: PROMIS Study Week Mapping

PROMIS assessment day (inclusive)	Study Week
≤ 4	Baseline
5 - 11	Week 0
12 - 18	Week 1
19 - 25	Week 2
26 - 32	Week 3
33 - 39	Week 4
40 - 46	Week 5
47 - 53	Week 6
54 - 60	Week 7
61 - 67	Week 8
68 - 74	Week 9
75 - 81	Week 10
82 - 88	Week 11
89 - 95	Week 12

The absolute values and change from baseline values for PROMIS SD SF 8b total T-scores and total raw scores will be summarized using descriptive statistics by study treatment and week. The change from baseline over time by study treatment will be shown using line plots for means and 95% CI. In addition, the number and percentage of each response for each individual item will be summarized using frequency tables by study treatment and week. Stacked bar charts will also be produced showing the composition of responses for each item by treatment group and week.

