- Population: Women aged 40–65 with sleep disturbance associated with the menopause, further defined by the key inclusion/exclusion criteria.
- Variable: Change from baseline in WASO measured by PSG at Week 4.
- Treatment: Elinzanetant 120 mg or placebo.
- ICEs and strategies: Important ICEs to consider are listed in Table 1–1.

Table 1-1: Primary Estimand: ICEs and Strategies to Address Them

ICEs	Proposed Strategy	Data Handling Method	Interpretation
Temporary study treatment interruption	Hypothetical	Discard data collected after the ICE	The treatment effect that would be if participants complied with treatment
Premature discontinuation of study treatment	Hypothetical	Discard data collected after the ICE	The treatment effect that would be if participants did not discontinue the randomized treatment
Intake of prohibited concomitant medication having impact on efficacy	Hypothetical	Discard data collected after the ICE	The treatment effect that would be if participants did not take prohibited concomitant medications impacting sleep

ICE = Intercurrent event.

 Population level summary: Mean change from baseline in WASO measured by PSG at Week 4

Overall Design Synopsis:

This is a multi-center, multi-country, double-blind, randomized, parallel-group, placebo-controlled, pilot intervention study in women with sleep disturbances associated with menopause.

Short Summary:

The purpose of this study is to assess efficacy and safety of elinzanetant on sleep disturbances associated with menopause. Study details include:

The study duration will be about 23 weeks (plus potential washout period).

The treatment duration will be approximately 12 weeks.

21 SEP 2023 Page: 13 of 73

The visit frequency will be once every 1–2 weeks during the screening period (depending on the scheduling of PSG) and once every 4–5 weeks during the intervention and follow-up periods.

Number of Participants:

Approximately 223 participants will be screened to achieve 78 participants to be randomized in a 1:1 ratio to investigational intervention. This will result in an estimated 70 participants (35 per study intervention) evaluable for the primary efficacy analysis.

Study Arms and Duration:

All participants will receive either 120 mg of elinzanetant or matching placebo orally once daily prior to going to sleep:

- Elinzanetant 120 mg for 12 weeks
- Placebo for 12 weeks

Treatment may be prolonged by up to 1 week to allow for scheduling of the sleep laboratory assessment at EoT.

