PGI-S i						>	
PGI-C ^j		-	Starts 1	weeks after	BL		
Study medication			Starts after	er the first dos	se of study r	medication	
intake documentation						>	
Collection of						•	
handheld device							

AE = adverse event, BL = baseline, eCOA = Electronic clinical outcome assessments, EoT = End of Treatment, ePRO = Electronic patient-reported outcome, FU = follow-up, IP = In person, IRT = Interactive response technology, PK = pharmacokinetics, PSG = polysomnography, SCR = screening, SoA = Schedule of activities, T = treatment.

Questionnaires: eC-SSRS = Electronic Columbia-Suicide Severity Rating Scale, GAD-7 = Generalized Anxiety Disorder Scale -7, HFDD = Hot Flash Daily Diary, ISI = Insomnia Severity Index, PGI-C = Patient Global Impression of Change, PGI-S = Patient Global Impression of Severity, PROMIS SD SF 8b = Patient-reported Outcomes Measurement Information System Sleep Disturbance Short Form 8b, SD = Sleep Diary.

21 SEP 2023 Page: 16 of 73

- a All screening evaluations should typically be completed within 4–6 weeks with at least 14 days between SCR-1 and SCR-2 and at least 7 days at home after SCR-2 and before BL. The time required for scheduling for PSG and central reading of PSG needs to be considered for visit planning.
 b All EoT assessments (except for the safety and PK sample) are performed in the morning after the second night in the PSG lab.
- **c** If a participant discontinues prematurely from treatment, an EoT visit will be performed as soon as possible; it will comprise all assessments scheduled for the EoT visit. The EoT visit will be followed after 4 weeks by the FU visit. The handheld device will be collected at the last scheduled IP visit.
- d Eligibility check on inclusion criterion 3 (HFDD) should be assessed prior to PSG.
- e Including consultation about results obtained from screening procedures.
- f PK sample is collected on the second day in the PSG lab together with the safety lab sample.
- **g** All PSGs scheduled for T1 and T3 need to be performed under treatment, i.e., the second PSG night at EoT needs to be performed at the latest during the night after the last capsule has been taken.
- **h** The PROMIS SD SF 8b will be collected at SCR-1 and weekly from BL until EoT.
- i The PGI-S will be collected weekly from SCR-2 until EoT.
- j The PGI-C will be collected weekly following the PGI-S from 1 week after BL until EoT.

2. Introduction

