4.3.2.2 Insomnia Severity Index (ISI)

The ISI is a 7-item instrument that quantifies the participants perception of insomnia severity in the last 2 weeks (Bastien et al, 2001) and is collected during screening, at week 4 and at week 12/EoT. The items refer to: severity of sleep onset, sleep maintenance and early morning wakening problems, satisfaction with sleep pattern, noticeability of sleep problems by others, distress caused by the sleep difficulties and interference of sleep difficulties with daytime functioning. It is scored on a 5-point Likert scale from 0 to 4. The scores for each

Version 2.0 Page: 28 of 57

item are summed to produce the total score (maximum of 28) which allow categorization of severity of insomnia.

Total score severity categories:

- 0-7 = No clinically significant insomnia
- 8–14 = Subthreshold insomnia
- 15–21 = Clinical insomnia (moderate severity)
- 22–28 = Clinical insomnia (severe)

The baseline value will be the earliest assessment on day 1 or day 2. If both day 1 and day 2 assessment is not available, the baseline value will be the latest available assessment on or before day 4. Only assessments where ≥ 8 days of the 14-day recall period are outside of the impact duration of prohibited hormonal therapies and medication potentially confounding efficacy will be included. Details regarding the prohibited medications together with the impact duration are described in Section 6.3.

The absolute values and change from baseline values for ISI total score will be summarized using descriptive statistics by study treatment and week. The change from baseline over time by study treatment will be shown using line plots for means and 95% CI.

The ISI severity categories will be summarized using frequency tables by study treatment and week. Stacked bar charts showing the composition of severity categories at each week by treatment group will be produced.

In addition, the number and percentage of each response for each individual item will be summarized using frequency tables by study treatment and week. Stacked bar charts will also be produced showing the composition of responses for each item by treatment group and week.

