6.4.2 Temporary treatment interruption

Temporary treatment interruption is defined as

- Treatment taken < 80% during day 1 to the last PSG night at week 4 (inclusive) OR treatment taken on < 5 days during the last 7 days up to the last PSG night at week 4 (inclusive) for week 4.
- Treatment taken < 80% during day 1 to the last PSG night at week 12 (inclusive) OR treatment taken on < 5 days during the last 7 days up to the last PSG night at week 12 (inclusive) for week 12.

If the week 4 PSG assessment is missing, day 30 will be used instead of the last PSG night in the definition of treatment interruption for week 4 only for participants who have not prematurely discontinue treatment prior to day 30. Similarly for week 12, day 86 will be used only for participants who have not prematurely discontinue treatment prior to day 86.

The criterion for treatment taken on 5/7 days during the corresponding week prior to and including the last PSG night, as defined above, is met, if treatment has been taken for less than 5 days (i.e., at least 3 missed intakes). To calculate the number of days per week with treatment intake, a day where at least one capsule was taken, will be considered as a day with treatment intake.

To identify whether < 80% treatment was taken, compliance up to and including the last PSG night at week 4 will be calculated as

100 * Number of capsules taken up to and including the last PSG night at week 4 / (2 * study duration up to and including the last PSG night at week 4)

Compliance up to and including the last PSG night at week 12 will be calculated as

100 * Number of capsules taken up to and including the last PSG night at week 12 / (2 * study duration up to and including the last PSG night at week 12)

Study duration up to and including the last PSG night at week 4 and week 12 is derived as the number of days from the day of first study intervention intake up to and including the last PSG night at week 4 and week 12 respectively. The number of capsules taken up to and including the last PSG night at week 4 and week 12 will be calculated based on the ePRO instrument 'Study medication intake documentation'. If the 'Study medication intake documentation' on the second PSG night at week 12/EoT is missing but the last treatment intake on the eCRF 'Study intervention' pages indicate that the participant took treatment on

Version 2.0 Page: 54 of 57

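### SAP Table 4-5 labels the end-of-treatment PROMIS and PGI forms Week 11 when the first Week 12 PSG night is day 85 or 86, so those participants have no Week 12 PROMIS value

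*SAP*

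**What the plan says.** Protocol section 1.3 sets T3/EoT at day 85 with a window of +7 days, and the synopsis explains the allowance: "Treatment may be prolonged by up to 1 week to allow for scheduling of the sleep laboratory assessment at EoT". Footnote b says that EoT assessments other than the safety and PK samples "are performed in the morning after the second night in the PSG lab". Footnote h fixes the PROMIS schedule: "The PROMIS SD SF 8b will be collected at SCR-1 and weekly from BL until EoT".

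SAP section 4.1.2 counts days 1 to 7 as study week 0, which makes Week 11 days 78 to 84 and Week 12 days 85 to 91. Section 4.3.2.1 maps weekly and EoT PROMIS forms alike: "an assessment will be assigned to that study week that covers the majority of the recall period". In Table 4-5, form days 82 to 88 are Week 11 and 89 to 95 are Week 12. When two forms fall in one week, "the latest available assessment will be used in the analysis". Section 4.3.2 adds: "No missing data imputation is planned for these endpoints". Section 4.4.5 applies the same mapping to PGI-S and PGI-C.

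Other measures from the same visit are tied to the visit. Scheduled PSG assessments count as Week 12 (section 4.2.1), and the ISI "is collected during screening, at week 4 and at week 12/EoT". For a missing Week 12 PSG, section 6.4.2 sets the default last PSG night: "Similarly for week 12, day 86 will be used only for participants who have not prematurely discontinue treatment prior to day 86".

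**The concern.** The recall rule is sensible for weekly forms while data collection continues. It fails at the end of treatment, because collection stops at the EoT visit and, on the earliest permitted dates, that visit comes before the first form day that Table 4-5 accepts as Week 12. No other rule places the EoT form in Week 12.

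Whether a woman who completed the form contributes to the Week 12 PROMIS endpoint then depends on when the sleep laboratory had a bed. One seen exactly on time drops out; one seen two days later counts. Her PSG from that visit and her ISI from that morning are both reported as Week 12.

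**Working it through.** **Inputs.** First PSG night s = 85 to 92 (Protocol 1.3). Last PSG night = s + 1, and EoT form day = s + 2 (footnote b). Study week = ceil(day/7) − 1 (SAP 4.1.2). Recall = the 7 days before the form day (the worked examples in SAP 4.3.2.1).

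**Reproducing the plan.** Day 8 has recall days 1–7, all in week 0, so week 0. Day 12 has recall days 5–11, 3 in week 0 and 4 in week 1, so week 1. Both match the SAP. The majority rule reproduces Table 4-5 for every form day from 5 to 95.

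**Applying it to the EoT visit.** The last column counts nights within days 85–91.

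| First PSG night | EoT form day | Recall days | Days in Week 11 / 12 | Table 4-5 label | Nights in Week 12 |
|---|---|---|---|---|---|
| 85 | 87 | 80–86 | 5 / 2 | Week 11 | 2 |
| 86 | 88 | 81–87 | 4 / 3 | Week 11 | 3 |
| 87 | 89 | 82–88 | 3 / 4 | Week 12 | 4 |
| 88 | 90 | 83–89 | 2 / 5 | Week 12 | 5 |
| 89 | 91 | 84–90 | 1 / 6 | Week 12 | 6 |
| 90 | 92 | 85–91 | 0 / 7 | Week 12 | 7 |
| 91 | 93 | 86–92 | 0 / 6 | Week 12 | 7 |
| 92 | 94 | 87–93 | 0 / 5 | Week 12 | 7 |

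**Can a weekly form fill the gap?** With weekly forms counted from day 1, one falls on day 85 (Week 11) and the next on day 92, after EoT for these starts. For s = 85 or 86 no form up to EoT falls on days 89–95, whichever of days 1 to 7 the weekly cycle starts from. Two forms then compete for Week 11. The later one (day 87 or 88) displaces the day 85 form, and Week 12 stays empty.

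**Week 4 is safe.** A T1 form on day 31 or 32 maps to Week 3, but treatment continues and the day 36 weekly form fills Week 4.

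**The nominal schedule.** A default last PSG night of day 86 means a first night on day 85 and an EoT morning on day 87, which is Week 11.

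**A related loss with a separate cause.** Weekly means for the sleep diary, HFDD and Sleepiz One+ need at least 4 days (SAP 4.4.2, 4.4.3, 4.6.3). The last column gives 2 and 3 nights for s = 85 and 86, so the Week 12 sleep diary, night-time HFDD and Sleepiz means are missing, as are the matching hot-flash-versus-WASO points. For the combined morning and evening HFDD, if the day 2–8 shift stated for week 0 carries through, Week 12 is diary days 86–92. The counts are then 1, 2, 3, 4, 5, 6, 7, 7, and three start days fail (85 to 87).

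**Effect on precision.** Let p be the share of participants starting on day 85 or 86 (an assumption). With 78 randomised and no dropout, n = 78(1 − p), and the interval widens by 1/√(1 − p):

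- p = 10%: n = 70.2, ratio 1.05
- p = 25%: n = 58.5, ratio 1.15
- p = 50%: n = 39, ratio 1.41

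**The case against.** Table 4-5 applies its stated rule correctly: a day 87 form has 5 of its 7 recall days in Week 11. That is true, but a 7-day recall rule combined with collection that ends at EoT leaves an on-time participant without a Week 12 value. Recall purity does not explain the difference from the ISI either. Completed on day 87, its 14-day recall covers days 73 to 86, of which 12 precede day 85, and it is still reported at Week 12.

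The impact is unknown. Two of eight start days is not a share of participants, day 86 is only a default for missing PSGs, and p could be near zero if visits run late. The SAP's version history says the PRO mapping was clarified during blinded programming, so the sponsor may have seen real visit dates. All of this stands, and it limits what can be said about size. It does not supply a missing rule.

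The harm is also modest. PROMIS is descriptive, no hypothesis is tested, the form is still tabulated under Week 11, and nothing links laboratory scheduling to treatment arm. So the loss is a smaller, schedule-dependent n, with no demonstrated bias between arms.

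Finally, day 85 could be read as the EoT morning, which would make four of eight days fail (forms on days 85 to 88). That reading sits badly with the day 86 default, so two of eight is the main figure.

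**Conclusion.** The point holds and should be fixed. On the SAP's own rules, a first Week 12 PSG night on day 85 or 86 leaves no Week 12 value for PROMIS, PGI-S or PGI-C, although the EoT forms were completed. PROMIS at Week 12 is a named secondary endpoint; the PGI endpoints are exploratory. The mapping result is certain given the visit window, the timing of EoT forms and the end of collection at EoT. The number of participants affected rests on visit dates that the documents do not give.

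Week 4 PROMIS, the PSG endpoints, the ISI, and the separate PSG-night summaries of the sleep diary and Sleepiz One+ are unaffected.

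**What to change.** Before unblinding, amend SAP sections 4.3.2.1 and 4.4.5 so that PROMIS, PGI-S and PGI-C forms completed at the scheduled T3/EoT visit are assigned to Week 12 by visit, as the scheduled PSG already is. The day 85 weekly form then fills Week 11. Keep Table 4-5 for all other weekly forms and, stated explicitly, for premature discontinuers, so that an EoT form on day 78 (recall days 71 to 77) is not called Week 12.

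For the Week 12 sleep diary, HFDD and Sleepiz One+ means, use the 7 nights (diary days) ending on the last PSG night. SAP section 6.4.2 already uses that window for treatment interruption, and section 4.8 explains that it was re-anchored because the visit may not fall at the end of the week.

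The cost is SAP wording and minor reprogramming; no new data are needed. There are small downsides to state. Week 12 PROMIS would be assigned by visit while Week 4 stays on Table 4-5. For a day 85 start, the Week 11 form (recall days 78–84) and the Week 12 form (80–86) share 5 of 7 recall days. The Week 12 diary window would be nights 80–86, of which 5 also lie in Week 11, and the Week 4 diary means would keep the calendar week.
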